### 12.5.2 Identification and Collection

Identification and collection of an AE begins after informed consent has been obtained and documented. Standard sources of identifying AEs include:

- direct observation by the Principal Investigator
- asking the Clinical Investigation participant a non-specific question (e.g., "Have you had any problems since the last visit?")

- volunteering of information by the Clinical Investigation participant (e.g., “Doctor, I have had blurred vision since I started using this lens.”)
- laboratory or test results that meet CIP requirements for classification as an AE.

All AEs, non-serious and serious, observed or elicited by the Principal Investigator, reported by the subject, or resulting from a test result, etc., occurring during the clinical investigation must be reported in the CRF. During the Clinical Investigation, the Principal Investigator should treat the Clinical Investigation subject as appropriate to ensure his/her safety and welfare.

Pre-existing conditions will not be considered AEs but will be collected at the Preoperative Visit as medical history. A worsening of a pre-existing condition during the Clinical Investigation should be documented as an (S)AE and evaluated accordingly.

Hospitalizations should be captured as a SAE until the cause of hospitalization can be identified. The following reports of hospitalization without a medical AE should not be considered either serious or an AE:

- Planned hospitalization for pre-existing condition, or a procedure required by the CIP, without a serious deterioration in health, is not considered a serious adverse event (e.g., for work-up of persistent pretreatment lab abnormality).
- Social admission (e.g., subject has no place to sleep)
- Administrative admission (e.g., for yearly physical exam)
- Optional admission not associated with a precipitating ocular medical AE (e.g., for elective cosmetic surgery)

### 12.5.3 Evaluations

When evaluating AEs, the Principal Investigator must determine if the event is serious, assess the severity of symptoms, and determine the relationship of the event to the device using the following guidelines:

#### a. Severity

- **Mild:** Subject awareness of a sign or symptom that is easily tolerated, requires no treatment, and does not interfere with subject’s daily activities
- **Moderate:** Subject awareness of a sign or symptom which may be a low level of concern to the subject and may interfere with daily activities, but can be relieved by simple therapeutic care
- **Severe:** A sign or symptom that interrupts the subject’s daily activity and requires systemic therapy or other treatment

#### b. Relationship to Investigational Medical Device or Control or Comparator IOLs or Surgical Procedure

- **Related:** There is at least a reasonable possibility the AE is related to the investigational medical device, control or comparator IOLs. or surgical procedure. Reasonable possibility means there is evidence to suggest either a causal relationship or association between the

investigational medical device, control or comparator IOLs or surgical procedure and the AE.

- **Unrelated:** There is little or no reasonable possibility the AE is related to the investigational medical device, control or comparator IOLs or surgical procedure. No reasonable possibility means there is no evidence to suggest either a causal relationship or association between the investigational medical device, control or comparator IOLs or surgical procedure and the AE.
- Classification of AEs that are serious (SAEs): The relationship to the Investigational Medical Device or Control or Comparator IOL is classified according to four different levels on the SAE Report Form: Not related, Possible, Probable, Causal relationship. The correlation between the four different levels on the SAE reporting form and the two different levels as defined above is described in the Safety Management Plan.

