### 12.5.1 Adverse Events Definitions

For the purposes of this Clinical Investigation, adverse events include: all serious and non-serious AEs; ocular adverse device effects (ADEs; Serious Adverse Device Effect (SADE). AEs, SAEs, ADEs and SADEs are defined as follows.

An adverse event (AE) is any untoward medical occurrence, unintended disease or injury, or untoward clinical sign (including abnormal laboratory finding) in a subject, user or other persons, whether or not related to the investigational medical device and whether anticipated or unanticipated. This definition includes events related to the investigational medical device, Control or Comparator IOLs or procedures involved. For users or other persons, this definition is restricted to events related to the Investigational medical device or Control or Comparator IOLs.

A Serious Adverse Event (SAE) is an AE that leads to:

- Death
- A serious deterioration in the health of the subject that either results in:
  - a life-threatening illness or injury, or
  - a permanent impairment of a body structure or body function (e.g., blindness), or
  - in-patient or prolonged hospitalization, or
  - a potentially vision-threatening condition, or
  - medical or surgical intervention to prevent life- or vision-threatening illness or injury or permanent impairment to a body structure or a body function
- fetal distress, fetal death, or a congenital abnormality or birth defect

An Adverse Device Effect (ADE) is any adverse event related to the use of an investigational medical device. This definition includes any events resulting from insufficient or inadequate instructions for use, deployment, implantation, installation or operation, or any malfunction of the investigational medical device. This definition also includes any event resulting from use error or from intentional misuse of the investigational medical device. This definition also includes Control and Comparator IOLs.

A Serious Adverse Device Effect (SADE) is any ADE which also meets any of the serious criteria for SAEs.

SADEs include the following:

- Unanticipated is a serious adverse device effect which by its nature, incidence, severity or outcome has not been identified in the current version of the Risk Analysis Report.
- Anticipated is a serious adverse device effect which by its nature, incidence, severity or outcome has been previously identified in the Risk Analysis Report.

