#### **13.2.1 Adverse Events**

All adverse events collected during the study will be recorded and classified on the basis of MedDRA terminology. Descriptions of AEs will include the affected eye(s), the date of onset, the date the AE ended, the severity of the AE, the relationship to test, comparator, or control lens, the action taken to treat the AE, and the outcome. All reported treatment-emergent AEs (TEAEs) will be summarized by the number of subjects reporting AEs, system organ class, severity, seriousness, and relationship to study medication. TEAEs are those AEs with an onset on or after the date of the first study surgery.

Adverse events will be summarized by treatment group and severity. Each subject will be counted only once within a system organ class or a preferred term by using the adverse events with the highest severity within each category.

Adverse events will be summarized by treatment group and relationship to test, comparator, or control lens. Each subject will be counted only once within a system organ class or a preferred term by using the adverse events with the greatest relationship within each category.

Comparisons among treatment groups will be made by tabulating the frequency of subjects with one or more AEs (classified into MedDRA terms) during the study.

All information pertaining to AEs noted during the Clinical Investigation will be listed by subject, detailing verbatim given by the Principal Investigator, preferred term, system organ class, start date, stop date, severity, actions taken, and device relatedness. The AE onset will also be shown relative (in number of days) to the day of initial study surgery.

Serious adverse events (SAEs) will be tabulated by subject within treatment groups.

In addition, a list of subjects who discontinued from the study and a list of subjects who experienced SAEs will also be provided.

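### The adverse event causality code merges lens and surgical procedure, so the planned summary by relationship to the lens would count purely surgical events as lens-related

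*Combined protocol and SAP*

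**What the plan says.** The lead-in to Section 12.5.3 asks about the device only. The investigator must "determine the relationship of the event to the device using the following guidelines".

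Item b of that section supplies the guidelines. *Related* means "There is at least a reasonable possibility the AE is related to the investigational medical device, control or comparator IOLs. or surgical procedure". *Unrelated* means "There is little or no reasonable possibility the AE is related to the investigational medical device, control or comparator IOLs or surgical procedure". No lens-only category and no separate procedure item is defined.

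For serious events the same item describes another scale: "The relationship to the Investigational Medical Device or Control or Comparator IOL is classified according to four different levels on the SAE Report Form". The procedure is not named there. The correlation between those four levels and "the two different levels as defined above is described in the Safety Management Plan", which is not among the documents.

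Section 13.2.1 sets the analysis: "Adverse events will be summarized by treatment group and relationship to test, comparator, or control lens". Each subject counts once per system organ class or preferred term, "using the adverse events with the greatest relationship within each category". The by-subject listing carries device relatedness. One sentence of the section names study medication as the causal target, although the trial tests lenses. No summary by relationship to the procedure is planned.

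Section 12.5.1 makes device status depend on causality: "An Adverse Device Effect (ADE) is any adverse event related to the use of an investigational medical device". The definition goes on to cover events arising from deployment, implantation and use error, and extends to the Control and Comparator lenses.

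**The concern.** The code and the table built on it answer different questions. The code asks whether the lens or the operation caused the event. The table claims to show whether the lens did. Every subject has both a lens and an operation, so the code cannot separate the two causes in anyone.

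This matters for how the safety results read. Evaluating safety is among the objectives in the Synopsis, and Section 12.4 anticipates harm specific to the Test lens, such as reduced quality of distance vision and possible explantation. A table of lens-related events should isolate such events. If it also holds wound complications, it overstates what the lenses did and is harder to interpret. Two further uses of causality are affected: identifying non-serious adverse device effects, and agreement between the SAE form and the adverse event database.

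**Working it through.** No sample size, rate or error level enters this point, so the check is a comparison of texts.

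**Step 1. Classify each possible cause under both definitions.** The two-level code comes from Section 12.5.3 b. The device-only answer is what the lead-in to Section 12.5.3, the SAE form and Section 13.2.1 call for.

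| Cause of the event | Two-level code | Device-only answer | Agree? |
|---|---|---|---|
| Lens only | Related | Related | Yes |
| Lens and procedure | Related | Related | Yes |
| Procedure only | Related | Not related | No |
| Neither | Unrelated | Not related | Yes |

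The two differ in one row. An example for that row is a wound leak that the investigator attributes to the incision alone. Wound leak is on the Section 12.5.1 list of anticipated events without an asterisk, so it is not subject to the reporting thresholds for expected postoperative findings.

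**Step 2. Carry the code into the table.** Within one system organ class or preferred term, the count labeled as related to the lens is the number of subjects with at least one *Related* event. The excess over the true lens-related count is the number of subjects who have a procedure-only event in that class or term and no lens-linked event there. It is zero or positive in every arm, so the table can only overstate.

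**Step 3. Check the link to the SAE scale.** The upper three SAE levels (possible, probable, causal) all imply a reasonable possibility of a device link, so they correspond to *Related*. The lowest level, not related, contains two rows of the table above: procedure only, which item b calls *Related*, and neither, which item b calls *Unrelated*. If that level maps to *Unrelated*, the procedure-only events break the item b definition. If it maps to *Related*, every SAE becomes related. Under the pooled definition, no mapping from level to level satisfies both. The cause is the difference in scope (procedure in or out), not the number of levels.

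**Step 4. Check device-effect status.** For a non-serious event the two-level code is the only causality code defined. *Related* covers three of the four rows, one of them with no lens link, so the code alone does not identify a non-serious device effect. A serious event also has the device-only SAE scale, and Table 2 in Section 12.5.4 routes SAEs by device relation, so serious device effects have their own source.

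**Step 5. Look for a size.** The documents give no expected rate of procedural or lens-related events in any arm, so the excess in Step 2 cannot be computed. Two features reduce it. Asterisked events in Section 12.5.1 are reported only above stated thresholds. Appendix C bars implantation after several intraoperative complications, so a subject who has one in the first eye and receives no study lens is outside the Safety set.

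**The case against.** The strongest reply is that item b states one standard to be applied to each possible cause in turn. The same chain of alternatives joins the three lens types, and nobody takes that as pooling them. The lead-in asks about the device, Section 13.2.1 lists relationship to the lens as the data item, and the header of Table 1 in Section 12.5.4 speaks of device and/or procedure relation, so the authors evidently had the distinction in mind. On this reading four device levels map to two device levels without conflict. The case report form and the Safety Management Plan are not in the documents and may already hold separate items.

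The reading is possible but strained. Each subject receives one lens type, so the alternatives among lenses pool nothing within a subject. Lens and procedure both apply to every subject, so that alternative does pool. The possibility that the form separates the two stands. It means that the miscount follows from the written plan and is not shown for the database.

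A reader might also infer three stronger things that the documents do not support:

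- *That pooling masks a difference between lenses or biases the comparison.* Section 13.2.1 compares groups by the frequency of subjects with any adverse event by MedDRA term, without using relatedness. The relationship summary is within class and term, so a wound event does not hide a visual symptom coded to another term. All arms have the same type of operation.
- *That neither adverse device effects nor serious ones can be determined.* Serious ones can be taken from the SAE form. The gap concerns non-serious events. Some operative events are also device effects by the Section 12.5.1 definition.
- *That the Safety Management Plan mapping is wrong.* It has not been seen. The conflict in Step 3 follows only if the pooled definition is applied as written.

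**Conclusion.** The point holds as a defect in the written plan. The only causality definition for adverse events covers lens or procedure, while the planned summary and listing are labeled as relationship to the lens. Events due to surgery alone would appear there as lens-related, the code alone would not identify non-serious device effects, and a serious procedure-only event would be classified differently on the two scales.

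The consequence is modest. Lens-related counts are inflated in any arm that has procedure-only events, by an amount that the documents do not allow to be estimated. No arm is inherently favored, and the primary endpoint, power and type I error are unaffected. The conclusion assumes that the code is used as Section 12.5.3 b defines it. If the case report form already separates the two causes, what remains is a correction of text.

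**What to change.** - For every adverse event, serious or not, record relationship to the lens and relationship to the surgical procedure as two separate items. If the case report form already does so, correct Section 12.5.3 b to match it.
- Use the lens item for the relationship summary in Section 13.2.1, for the device-relatedness listing and for the mapping from four SAE levels to two. State that mapping in the plan.
- Classify adverse device effects and serious adverse device effects from the lens item read together with the Section 12.5.1 definition, so that events from deployment, implantation and use error are handled as that definition requires.
- Add a parallel summary by relationship to the procedure.
- In Section 13.2.1, replace the reference to study medication with study lens.

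The cost is at most one case report form field and one descriptive table.

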#### 12.5.4 Reporting

Actions required by the Principal Investigator for reporting non-serious adverse events are summarized in [Table 1](#) below.

**Table 1. Non-serious Adverse Events**

	Non-serious AEs, device and/or procedure related or not related	Device-deficiency
Required Action	Recorded on Adverse Event CRF; no expedited report to Sponsor; Report to IRB/IEC and Regulatory Authority, as required per local regulations	Recorded on Device Deficiency Form; expedited report to Sponsor; no report to IRB/IEC

Actions required by the Principal Investigator for reporting all serious adverse events are summarized in [Table 2](#) below.

**Table 2. Serious Adverse Events**

SAEs	Non-device/non-device deficiency related	Device-and/or/Device deficiency related
Required Action	Recorded on SAE Report Form and AE CRF ↓ Principal Investigator submits expedited report to Sponsor or its representative within 24 hours; Report only to IRB/IEC and Regulatory Authority, as required per local regulations.	Recorded on SAE Report Form and AE CRF ↓ Principal Investigator submits expedited report to Sponsor or its representative within 24 hours; Principal Investigator reports to IRB/IEC and Regulatory Authority as required per local regulations.
		Sponsor Conducts Evaluation ↓ Sponsor or its representative reports Regulatory Authority within the timelines required by local regulations, as described in the Safety Management Plan.

#### 12.5.4.1 SAE, Reporting

The Principal Investigator must report any adverse event to the Sponsor and its representative in an expedited manner if it meets the criteria for an SAE/SADE, and any available supporting documents to the Sponsor or its designee within 24 hours of becoming aware of an event.

The Principal Investigator must also report SAE/SADE to the reviewing IRB/IEC and Regulatory Authority as required by local regulations. The Principal Investigator should also complete applicable CRFs within 3 working days of event identification. After first being informed by the Principal Investigator, the Sponsor or its representative will report the SADE to the Regulatory

Authority within the timelines required by local regulations, as described in the Clinical Investigation Safety Management Plan.

#### **12.5.4.2 Reporting Device Deficiencies**

A device deficiency is defined as an inadequacy of a medical device with respect to its identity, quality, durability, reliability, safety or performance. Device deficiencies include malfunctions, use errors, and inadequate labeling.

Principal Investigator must evaluate, record, and report any complaints/deficiencies or malfunctions experienced with an investigational medical device or Control or Comparator lens during this trial to the Sponsor and its representative promptly. The Sponsor shall review all device deficiencies, and, upon the Sponsor's request, Principal Investigator must supply any additional information related to the safety reporting of a particular event.

If the device deficiency is associated with or caused an SAE, then the SADE reporting procedure and timelines must be followed as per Section [12.5.4](#) in addition to device deficiency reporting procedures.

If no SADE was associated with or caused by the device deficiency but the deficiency might have led to a SADE if suitable action had not been taken or intervention had not been made or if the circumstance had been less fortunate, then deficiency needs to be reported within 24 hours of awareness and further reporting requirements to Regulatory Authority or to IRB/IEC need to be followed as applicable.

Any deficiency related to marketed products, including provided ancillary medical devices should be reported by the Principal Investigator to the sponsor or its representative as described above and to the Regulatory Authority, and to other parties in accordance with local requirements.

Details for submission of device deficiencies to sponsor or its representative are described in the Device Deficiency Reporting Form.

#### **12.5.5 Adverse Events at Subject Exit**

Ongoing AEs will be followed until resolution, no further change in the condition is expected (i.e., event stabilized), or as dictated by standard of care. Documentation in the CRF of this follow-up is not required although subject care should continue as appropriate. The Principal Investigator can issue a prognosis note and stop following ongoing and not stabilized adverse events 30 days or later after Post-op Visit 3 or day of early discontinuation if medically adequate.

Ongoing SAE/SADEs will be followed by the Sponsor and its representative(s) and documented by the Principal Investigator until the outcome is determined or until no further change in the condition is expected.

#### **12.5.6 Pregnancy**

During the Clinical Investigation, all female subjects of childbearing potential should be instructed to contact the Principal Investigator immediately if they suspect they might be pregnant (e.g., missed or late menstrual period). The Principal Investigator will report the pregnancy to the

sponsor or its representative on the Pregnancy Questionnaire within 48 hours of awareness. Female subjects who become pregnant during the Clinical Investigation will be followed until completion of pregnancy. Every effort will be made to obtain the health status of the mother and infant or fetus (in cases of miscarriage or therapeutic abortion) at term. Pregnancy itself is not considered an AE.

## 13 Statistics

### 13.1 Assessment of Performance

Performance will be assessed using the Intent-to-Treat (ITT) set.

#### 13.1.1 Primary Performance

##### 13.1.2 Binocular DCIVA

Hypotheses will be evaluated hierarchically in a fixed sequence as follows. The second test will be valid only if the first comparison results in rejection of the null hypothesis.

1. Superiority of the Test lens to the Control lens will be evaluated.
2. Noninferiority of the Test lens compared to the Active Comparator lens will be evaluated.

The Test lens will be compared to the Control lens using a two sample t-test with a one-sided alpha risk of 0.05. The null hypothesis ( $H_0$ ) for this comparison is that the mean DCIVA of the Test lens ( $\mu_T$ ) is greater than or equal to the mean DCIVA of the Control lens ( $\mu_C$ ). The alternative hypothesis ( $H_1$ ) is that the mean of the Test lens is less than the mean of the Control lens.

$$\begin{aligned}H_0: \mu_T &\geq \mu_C \\H_1: \mu_T &< \mu_C\end{aligned}$$

If the null hypothesis is rejected, then the Test lens will be statistically superior to the Control lens and the Clinical Investigation will be statistically successful.

If the first null hypothesis is rejected, then noninferiority the Test lens compared to the Active Comparator lens will be evaluated. The null hypothesis ( $H_0$ ) is that the difference between the mean DCIVA of the Test lens ( $\mu_T$ ) and the mean DCIVA of the Active Comparator lens ( $\mu_{AC}$ ) is at least 0.1. The alternative hypothesis ( $H_1$ ) is that the difference is less than 0.1.

$$\begin{aligned}H_0: \mu_T - \mu_{AC} &\geq 0.1 \\H_1: \mu_T - \mu_{AC} &< 0.1\end{aligned}$$

A two-sided 90% confidence interval will be constructed around the estimate of the difference between treatments as for a two-sample t-test. If the upper confidence limit is less than 0.1, then the Test lens will be statistically significantly noninferior to the Active Comparator lens.

The primary endpoint tests will be repeated as sensitivity analyses with the Per Plan (PP) set.

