### **9.2 Concomitant Medications and Treatments**

Documentation of all medications and treatments used by the subject within 30 days prior to informed consent and during the Clinical Investigation will be made in Clinical Investigation source documents.

Pre-, intra-, and postoperative medications and treatments may be administered per the Principal Investigator's standard of care. A complete list of the Principal Investigator's standard regimen of these medications and treatments will be provided to the Sponsor or its designee prior to initiation of the Clinical Investigation. Standard of care medications and treatments used according to the standard site regimen will not be recorded as Concomitant Medications in the electronic data capture (EDC) system. Only viscoelastics as decided by the sponsor are allowed during cataract surgeries (see [APPENDIX C](#)).

Medications and Treatments known to interfere with visual performance, pupil dilation, or iris structure are prohibited within 30 days of enrollment and for the duration of the Clinical Investigation.

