### **13.7.2 Sample Size Determination**

Estimates of treatment effects and the standard deviation for the primary endpoint were obtained from published studies of the Active Comparator lens. Sample size calculations were completed using nQuery software, Version 9 (Statistical Solutions Ltd.).

**Superiority Versus the Control Lens:** A two group t-test with a 5% one-sided significance level will have 93% power to detect a difference in means of -0.14, assuming that the common standard deviation is 0.15, when the sample sizes in the two groups are 29 and 20, respectively (a total sample size of 49).

**Noninferiority Versus the Active Comparator lens:** When the sample size in each group is 29, a two group one-sided 0.05 significance level t-test will have 80% power to reject the null hypothesis that the test treatment is not non-inferior to the active comparator (the difference in means,  $\mu_T - \mu_{AC}$ , is 0.1 or greater) in favor of the alternative hypothesis that the test lens is non-inferior to the active comparator, assuming that the expected difference in means is 0 and the common standard deviation is 0.15.

To allow for 2% dropouts approximately 80 subjects will be enrolled.

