#### **5.0 PUPIL SIZE**

Pupil size will be measured with a pupillometer at the corneal plane to the nearest 0.1 mm. Eye illumination for pupil measurement will be identical to the photopic and mesopic illumination used for visual acuity testing – 85 ( $\pm 2$ ) cd/m^2 and 3 ( $\pm 0.5$ ) cd/m^2, respectively. If lighting conditions are unable to be used or lighting conditions that vary slightly from these target illuminations are to be used, they should be discussed with the Sponsor for approval. Pupil measurement will be initiated only after the eye has had time to fully adapt to the testing conditions (approximately 10 minutes). Pupil measurements are taken at screening Visit.

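### Both primary t-tests in 13.1.2 are valid but unadjusted; prespecified adjustment for preoperative pupil size and age would probably add a few points of power, mainly for noninferiority, conditional on an R² the documents do not give

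*Combined protocol and SAP*

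**What the plan says.** Section 13.1.2 sets two tests in fixed sequence on binocular distance-corrected intermediate acuity (DCIVA) at Visit 3.

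- Superiority to Control: "The Test lens will be compared to the Control lens using a two sample t-test with a one-sided alpha risk of 0.05".
- Noninferiority to the Active Comparator: "A two-sided 90% confidence interval will be constructed around the estimate of the difference between treatments as for a two-sample t-test". The decision rule is: "If the upper confidence limit is less than 0.1, then the Test lens will be statistically significantly noninferior to the Active Comparator lens".

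The Synopsis agrees. Section 13.4 only summarizes baseline characteristics by group. The sensitivity analysis in 13.1.2 repeats the same tests in the Per Plan set. Section 13.1.4 is redacted, so an adjusted exploratory analysis cannot be ruled out, but the primary tests are fully readable.

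Two candidate covariates are available before surgery. Section 11.1.1 collects demographics at Visit 0, and age is inclusion criterion 1. On the pupil, Appendix B section 5.0 says "Eye illumination for pupil measurement will be identical to the photopic and mesopic illumination used for visual acuity testing" and "Pupil measurements are taken at screening Visit".

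Section 13.7.2 plans the first test as follows: "A two group t-test with a 5% one-sided significance level will have 93% power to detect a difference in means of -0.14". That figure takes 29 Test and 20 Control subjects and an SD of 0.15 in both arms. The noninferiority test is planned at 80% power with 29 per arm, a true difference of 0 and the same SD.

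**The concern.** The plan takes trouble over the pupil. It measures pupil size in the light used for acuity testing, excludes abnormal dilation and eccentric pupils (8.2, criteria 14 and 20), and restricts drugs: "Medications and Treatments known to interfere with visual performance, pupil dilation, or iris structure are prohibited within 30 days of enrollment". The primary analysis then makes no use of the measurement, or of age.

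With 20 to 30 subjects per arm and no stratification in the readable allocation text (9.1.1), balance on these variables is left to chance. If they are related to intermediate acuity, an unadjusted comparison carries variance that could be removed. The noninferiority test has most to gain, since it is planned at only 80% power and counts only if superiority has succeeded. Simulated power to pass both tests under the plan's assumptions is about 77%.

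**Working it through.** **Inputs.** From 13.7.2: SD 0.15; Test 29, Active Comparator 29, Control 20 (78 evaluable); one-sided alpha 0.05; superiority difference 0.14; noninferiority margin 0.1 with true difference 0. Assumed, because the documents give no figure: R² of pupil size and age together with DCIVA, over the range 0 to 0.20.

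**Step 1: reproduce the plan.** SE = SD × √(1/n₁ + 1/n₂); power is from the noncentral t distribution with noncentrality difference/SE.

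- Superiority: SE = 0.15 × √(1/29 + 1/20) = 0.0436; noncentrality 0.14/0.0436 = 3.21; df 47; power 93.6% (stated 93%).
- Noninferiority: SE = 0.15 × √(2/29) = 0.0394; noncentrality 0.1/0.0394 = 2.54; df 56; power 80.6% (stated 80%).

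**Step 2: add two covariates.** The residual SD becomes 0.15 × √(1 − R²). Estimating two slopes when the covariates are imbalanced by chance inflates the variance of the contrast by about 1 + 2/(residual df − 1):

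- three-arm model: residual df 78 − 3 − 2 = 73, factor 1 + 2/72 = 1.028;
- pairwise, Test and Control: df 45, factor 1 + 2/44 = 1.045;
- pairwise, Test and Active Comparator: df 54, factor 1 + 2/53 = 1.038.

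Example, pairwise noninferiority at R² 0.10: SD = 0.15 × √0.90 = 0.1423; SE = 0.1423 × √(2/29) × √1.038 = 0.0381; noncentrality 2.63; power 82.9%.

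**Step 3: results (superiority / noninferiority).** The three-arm column uses the model-based pooled SE.

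| R² | Three-arm ANCOVA | Pairwise ANCOVA |
|---|---|---|
| 0 | 93.2% / 79.8% | 92.6% / 79.3% |
| 0.05 | 94.2% / 81.6% | 93.7% / 81.0% |
| 0.10 | 95.2% / 83.4% | 94.7% / 82.9% |
| 0.20 | 96.9% / 87.1% | 96.5% / 86.6% |
| Planned t-tests | 93.6% / 80.6% | 93.6% / 80.6% |

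Break-even is at R² of about 0.02 for the three-arm model. For the pairwise model it is just under 0.05. At R² = 0 the three-arm model loses about 0.3 and 0.8 points; the pairwise model loses 93.6 − 92.6 = 1.0 and 80.6 − 79.3 = 1.3 points.

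Simulation (20,000 runs per R²) agrees with the three-arm column. Power to pass both tests with that model is 76%, 79%, 81% and 86% at R² 0, 0.05, 0.10 and 0.20, against about 77% for the t-tests.

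**Step 4: is pooling three arms safe?** Pooling the SD without covariates adds only about 0.2 points (93.8% and 80.8%). With a common SD, as the plan assumes, type I error stays at 5%. With unequal SDs (assumed, R² 0.10) the pooled three-arm model does worse than the planned tests:

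- Control SD half the others: noninferiority type I error rises from 4.9% to 6.7%.
- Control SD 1.5 times the others: superiority type I error rises from 6.4% to 7.5%.

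In the first case, an ANCOVA fitted only to the two arms compared gives 5.0% for noninferiority, and the three-arm model with HC3 standard errors gives 4.6%. HC3 costs some power, so the three-arm column is somewhat optimistic for that version.

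**The case against.** The strongest reply is that nothing is broken. The t-test is unbiased under randomization, it matches the sample-size calculation, and trial success rests on superiority, which already has 93% power. No section links pupil size or age to DCIVA. The drug restriction in 9.2 covers visual performance in general and is not tied to the endpoint. Excluding abnormal pupils may narrow the range of pupil sizes and so lower R². The pupil is measured before cataract surgery, the outcome at Visit 3.

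All of that stands, and it limits the point to an efficiency suggestion whose benefit is conditional. It does not remove the suggestion, because the stakes are uneven: about 1 point of noninferiority power at risk against gains of 82.9 − 80.6 = 2.3 points (R² 0.10) or 86.6 − 80.6 = 6.0 points (R² 0.20) with the pairwise model.

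Three stronger readings are tempting and not supported:

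- A reader might infer that adjustment is free. It is not. Estimating the slopes costs precision, and power falls if the covariates explain almost nothing.
- A reader might infer that each t-test is deficient because it leaves out the third arm when estimating the SD. That is worth about 0.2 points, and leaving it out protects the noninferiority interval from the Control arm's variance.
- A reader might infer that no practical detail is involved. Section 13.7.3 rules out imputation, so a subject without a pupil reading would leave an adjusted model, and Appendix B 5.0 allows sponsor-approved departures from the target lighting.

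**Conclusion.** The point holds as a low-cost improvement in efficiency. It does not show an error, a bias or a shortfall in planned power. Both primary tests ignore two baseline variables that the trial already collects. If those variables explain 10% to 20% of the DCIVA variance, a pairwise ANCOVA raises noninferiority power from 80.6% to between 82.9% and 86.6%, and superiority power from 93.6% to between 94.7% and 96.5%. If they explain less than about 2% (three-arm) to 5% (pairwise), power falls slightly, by at most 1 to 1.3 points for the pairwise model.

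The figures rest on the plan's SD of 0.15, 78 evaluable subjects, linear covariate effects common to all arms, and an R² range that is assumed. The gain comes from the covariates and not from pooling arms.

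**What to change.** Before any unmasked data are reviewed, amend 13.1.2 and the Synopsis as follows.

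1. Make the primary model an ANCOVA of Visit 3 binocular DCIVA on treatment, preoperative photopic pupil diameter (mean of both eyes) and age. Fit it to the two arms being compared, or to all three arms with HC3 standard errors. Name one of these.
2. Take the one-sided 0.05 Test–Control test and the two-sided 90% interval for Test minus Active Comparator from that model. Leave the margin and the fixed sequence unchanged.
3. State what happens to a subject with a missing pupil reading, or one taken outside the target lighting, so that no one drops out of the primary analysis by default.
4. Keep the unadjusted t-tests as a sensitivity analysis. The unequal-variance form is preferable, because the pairwise ANCOVA still assumes equal SDs within each pair, and the Test–Control comparison has unequal group sizes.

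Timing matters because the sponsor is unmasked (9.1.1.1) and interim summaries by treatment group are permitted (13.6), so covariates chosen later could look data-driven. The change needs SAP wording only, with no new measurements or subjects. Its price is the small loss of power if the covariates turn out to be uninformative.
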